- Missing end day and month, but year present: If the maximum of the subject's date of study termination or the date equivalent to 70 days after the subject's last intake of study medication is the same year as the occurrence of the AE/Concomitant medication, then the end day and month will be set to the maximum of the date of study termination or the date equivalent to 70 days after last intake of study medication. Otherwise the end day will be set to December 31st of the given year.

Efficacy variables

The start and end dates of flares will be imputed for the analyses of AU flares data, in order to allow the calculation of time intervals between 2 consecutive flares and the duration of flares. Different rules will be applied for pre-study and on-study period flares.

For the interim analysis, the pre-study period is starting 48 weeks prior to Baseline, i.e. 336 days prior to Baseline until Baseline. The on-study period for the interim analysis is starting from Baseline until week 48, i.e. until study day 336.

For the final analysis, the pre-study period is starting 24 months prior to Baseline, i.e. 730 days prior to Baseline until Baseline. The on-study period for the final analysis is starting from Baseline until week 96, i.e. until the date of the Week 96 or discontinuation visit. In addition, sensitivity and supportive analyses use different definitions (as defined in Section 8.1.2).

Pre-study period:

- Missing start day, but month and year present: Impute the first day of the month unless one of the following conditions apply:
 - Month and year are the same as month and year of the start date of pre-study period, then impute with the start date of pre-study period.
 - Month and year are the same as month and year of the end date of previous flare in the same eye, and the end date is clearly greater than end date of previous flare, then impute with the end date of previous flare.
 - In the case that month and year of the start date of pre-study period is the same month and year of the end date of previous flare in the same eye, then use the latest date of both for imputation.
- Missing start day and month, but year present: Impute January 1st unless one of the following conditions apply:
 - Year is the same as year of the start date of pre-study period, then impute with the start date of pre-study period.
 - Year is the same as year of the end date of previous flare in the same eye, then impute with the end date of previous flare.

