 - In the case that year of the start date of pre-study period is the same year of the end date of previous flare in the same eye, then use the latest date of both for imputation.
- Completely missing start dates of flares will only be imputed if it is clear based on the end date that the flare occurred within the pre-study period. Then the maximum (latest) of start date of pre-study period and end date of previous flare will be considered.
- Missing end day, but month and year present: Impute the last day of the month unless one of the following conditions apply:
 - Month and year are the same as month and year of the end date of pre-study period, then impute with the end date of pre-study period.
 - Month and year are the same as month and year of the start date of subsequent pre-study flare in the same eye before Baseline, then impute with the start date of subsequent pre-study flare.
 - In the case that month and year of the end date of pre-study period is the same month and year of the start date of subsequent pre-study flare in the same eye, then use the earliest date of both for imputation.
- Missing end day and month, but year present: Impute December 31st unless one of the following conditions apply:

- Year is the same as year of the end date of pre-study period, then impute with the end date of pre-study period.
- Year is the same as year of the start date of subsequent pre-study flare in the same eye, then impute with the start date of subsequent pre-study flare.
- In the case that year of the end date of pre-study period is the same year of the start date of subsequent pre-study flare in the same eye, then use the earliest date of both for imputation.
- Completely missing end dates of flares will only be imputed if it is clear based on the start date that the flare occurred within the pre-study period (of 2 years prior to baseline). Then the minimum (earliest) of end date of pre-study period (i.e. the day prior to treatment start date), the day prior to start date of subsequent pre-study flare in the same eye, or the start date plus the median duration of flare in that subject will be considered. The median duration of flare is determined from all flares recorded for that subject that have complete start and end dates (regardless of eye), including any flares prior to or during the pre-study period and on-study period.

On-study period (Baseline until end of treatment):

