- Missing start day, but month and year present: Impute the first day of the month unless one of the following conditions apply:
 - Month and year are the same as month and year of the start date of study medication, then impute with the start date of study medication.
 - Month and year are the same as month and year of the end date of previous on-study flare in the same eye, and the end date is clearly greater than end date of previous on-study flare in the same eye, then impute with the end date of previous on-study flare in the same eye.
 - In the case that month and year of the start date of study medication is the same month and year of the end date of previous on-study flare in the same eye, then use the latest date of both for imputation.
- Missing start day and month, but year present: Impute January 1st unless one of the following conditions apply:
 - Year is the same as year of the start date of study medication, then impute with the start date of study medication.
 - Year is the same as year of the end date of previous on-study flare in the same eye, then impute with the end date of previous on-study flare in the same eye.
 - In the case that year of the start date of study medication is the same year of the end date of previous on-study flare in the same eye, then use the latest date of both for imputation.
- Completely missing start dates of flares will only be imputed if it is clear based on the end date that the flare occurred after treatment start during the on-study period. Then the maximum (latest) of start date of study medication and end date of previous on-study flare in the same eye will be considered.

- Missing end day, but month and year present: Impute the last day of the month unless one of the following conditions apply:
 - Month and year are the same as month and year of the end date of on-study period, then impute with the end date of on-study period.
 - Month and year are the same as month and year of the start date of subsequent on-study flare in the same eye, then impute with the start date of subsequent on-study flare in the same eye.
 - In the case that month and year of the end date of on-study period is the same month and year of the start date of subsequent on-study flare in the same eye, then use the earliest date of both for imputation.
- Missing end day and month, but year present: Impute December 31st unless one of the following conditions apply:

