8.1.1 Derivations of primary efficacy variable

The primary efficacy variable is the number of distinct episodes of AU flares in the Treatment Period. Per protocol, a flare is considered a new episode if a gap of at least 3 months occurs between 2 flares. If AU flare episodes as reported by the investigator occur less than 3 months

(90 days) apart in the same eye, these will be programmatically corrected, such that a new AU flare within 3 months (90 days) after the end of the previous AU flare in the same eye will be considered as pertaining to the same AU episode. These flares will then be counted as one episode. Otherwise, if the time interval between 2 consecutive AU flares is greater than 3 months (90 days), or a separate eye is affected, the AU flares will be considered as separate episodes.

Pre-study and on-study AU flare episodes will be counted. An episode of AU flares is considered as pre-study, if the start date of flare is before the start date of study medication and if start date of flare occurs within the 24 months (730 days) prior to the start of study medication. For the interim analysis, an episode of AU flares is considered as pre-study if the flare occurs within 48 weeks (336 days) prior to the start of study medication.

For the Week 96 (primary) analysis, an episode of AU flares is considered on-study, if the start date of flare is on or after the start date of study medication and the start date of the flare occurs up to and including the last visit in the treatment period, i.e. Week 96 or discontinuation visit.

Pre-study and on-study flares of the same eye will be combined if the time interval between the end of pre-study flare and the start of subsequent on-study flare is less than 3 months (90 days). The resulting flare episode will be considered as pre-study flare episode.

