8.3.1 Flare assessments

For each subject in FAS, the total duration and the maximum severity of pre-study and on-study AU flares will be determined and summarized. The duration of an episode of AU flare (T_{Dur_Fl}) is calculated as follows:

$$T_{Dur_Fl} = Date_{End_Fl} - Date_{Start_Fl} + 1$$

with $Date_{End_Fl}$ and $Date_{Start_Fl}$ the end date and start date of flare, respectively. The duration of pre-study and on-study periods is defined in Section 4.2.

For the interim analysis, the pre-study period is starting 48 weeks prior to Baseline, i.e. 336 days prior to Baseline until Baseline. The on-study period for the interim analysis is starting from Baseline until week 48, i.e. until study day 336.

For the final analysis, the pre-study period is starting 24 months prior to Baseline, i.e. 730 days prior to Baseline until Baseline. The on-study period for the final analysis is starting from Baseline until week 96, i.e. until the date of the Week 96 or discontinuation visit.

The highest grade (severity) of uveitis flare across all flares per subject will be summarized. The highest grade (severity) noted during an episode of uveitis will be graded as follows: Grade 0=None; Grade 1+=Faint; Grade 2+=Moderate, iris and lens details clear; Grade 3+=Marked, iris and lens details hazy; Grade 4+=Intense, fibrin or plastic aqueous; ND=Not done or not assessed; UNK=Unknown

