 - Month and year are the same as month and year of the end date of pre-study period, then impute with the end date of pre-study period.
 - Month and year are the same as month and year of the start date of subsequent pre-study flare before Baseline, then impute with the start date of subsequent pre-study flare.
In the case that month and year of the end date of pre-study period is the same month and year of the start date of subsequent pre-study flare, then use the earliest date of both for imputation.
- Missing end day and month, but year present: Impute December 31st unless one of the following conditions apply:
 - Year is the same as year of the end date of pre-study period, then impute with the end date of pre-study period.

- Year is the same as year of the start date of subsequent pre-study flare, then impute with the start date of subsequent pre-study flare.
- In the case that year of the end date of pre-study period is the same year of the start date of subsequent pre-study flare, then use the earliest date of both for imputation.

Completely missing end dates of flares will only be imputed if it is clear based on the start date that the flare occurred within 12 months prior to treatment start. Then the minimum (earliest) of end date of pre-study period and start date of subsequent pre-study flare will be considered.

Has been changed to:

The start and end dates of flares will be imputed for the analyses of AU flares data, in order to allow the calculation of time intervals between 2 consecutive flares and the duration of flares. Different rules will be applied for pre-study and on-study period flares.

For the interim analysis, the pre-study period is starting 48 weeks prior to Baseline, i.e. 336 days prior to Baseline until Baseline. The on-study period for the interim analysis is starting from Baseline until week 48, i.e. until study day 336.

For the final analysis, the pre-study period is starting 96 weeks prior to Baseline, i.e. 672 days prior to Baseline until Baseline. The on-study period for the final analysis is starting from Baseline until week 96, i.e. until study day 672. In addition, the period definition used for interim with period length of 48 weeks will be repeated for the final analysis.

Pre-study period (48 vs 96 weeks prior to Baseline, i.e. 336 vs 672 days prior to Baseline, until Baseline for interim vs final analysis):

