- Missing start day, but month and year present: Impute the first day of the month unless one of the following conditions apply:
 - Month and year are the same as month and year of the start date of pre-study period, then impute with the start date of pre-study period.
 - Month and year are the same as month and year of the end date of previous flare, and the end date is clearly greater than end date of previous flare, then impute with the end date of previous flare.
 - In the case that month and year of the start date of pre-study period is the same month and year of the end date of previous flare, then use the latest date of both for imputation.
- Missing start day and month, but year present: Impute January 1st unless one of the following conditions apply:
 - Year is the same as year of the start date of pre-study period, then impute with the start date of pre-study period.
 - Year is the same as year of the end date of previous flare, then impute with the end date of previous flare.
 - In the case that year of the start date of pre-study period is the same year of the end date of previous flare, then use the latest date of both for imputation.

- Completely missing start dates of flares will only be imputed if it is clear based on the end date that the flare occurred within **the pre-study period**. Then the maximum (latest) of start date of pre-study period and end date of previous flare will be considered.
- Missing end day, but month and year present: Impute the last day of the month unless one of the following conditions apply:
 - Month and year are the same as month and year of the end date of pre-study period, then impute with the end date of pre-study period.
 - Month and year are the same as month and year of the start date of subsequent pre-study flare before Baseline, then impute with the start date of subsequent pre-study flare.
 - In the case that month and year of the end date of pre-study period is the same month and year of the start date of subsequent pre-study flare, then use the earliest date of both for imputation.
- Missing end day and month, but year present: Impute December 31st unless one of the following conditions apply:
 - Year is the same as year of the end date of pre-study period, then impute with the end date of pre-study period.
 - Year is the same as year of the start date of subsequent pre-study flare, then impute with the start date of subsequent pre-study flare.

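### A flare with a known end date but no start date has no cap on its imputed length, so one historical flare can be recorded as lasting up to 730 days and can be merged with the preceding same-eye flare

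*SAP*

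**What the plan says.** The rule is in SAP 4.2, under efficacy variables, pre-study period. It applies only when day, month and year of the start are all missing: "Completely missing start dates of flares will only be imputed if it is clear based on the end date that the flare occurred within the" window before first dose. The imputed date is then set as follows: "Then the maximum (latest) of start date of pre-study period and end date of previous flare will be considered". The same sentence appears in the amendment log in SAP section 13, but the current text of 4.2 is what governs.

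The window is also set in 4.2: "For the final analysis, the pre-study period is starting 24 months prior to Baseline, i.e. 730 days prior to Baseline until Baseline". For the interim analysis it is 336 days.

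The on-study counterpart in 4.2 reads "Then the maximum (latest) of start date of study medication and end date of previous on-study flare in the same eye will be considered". It restricts the previous flare to the same eye; the current pre-study sentence does not.

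The mirror case, a completely missing pre-study end date, is handled differently. It takes the earliest of the end of the window, the day before the next same-eye flare, "or the start date plus the median duration of flare in that subject will be considered". SAP 8.1.2 also repeats the primary analysis without subjects who have such flares. Completely missing start dates have neither the cap nor the sensitivity analysis.

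The imputed dates are used in two places. SAP 8.1.1 sets the merging rule: "a new AU flare within 3 months (90 days) after the end of the previous AU flare in the same eye will be considered as" part of one episode. SAP 8.3.1 states that "the total duration and the maximum severity of pre-study and on-study AU flares will be determined and summarized", with duration equal to end minus start plus 1.

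**The concern.** The rule gives the flare the earliest start that the window and the previous flare allow. For a condition that comes in discrete episodes, this fills the whole unknown interval with active disease.

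Three results come from the imputation rather than the data:

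- Historical flare-days are inflated, which flatters CZP on flare duration, a stated objective.
- Two distinct historical episodes can be counted as one, which works against CZP in the primary comparison.
- On study, a start set to the first dose can pull a flare into a recent same-eye pre-study episode. SAP 8.1.1 then counts the combined episode as pre-study, which favours CZP.

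Pre-study history is retrospective and reaches back 2 years. On-study flares are asked about at every visit, and both dates are requested (Protocol 9.1.1). The rule is therefore likely to act mainly on the historical side.

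**Working it through.** **Convention.** Day 0 is the first dose, and earlier days are negative. A same-eye gap under 90 days is taken as merging.

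**Window.** 2 × 365 = 730 days (final) and 48 × 7 = 336 days (interim), both as the SAP states.

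**Longest imputed flare.** Start = latest of (Day -730, end of previous flare); duration = end - start + 1.

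- No earlier flare, end on Day -1: -1 + 730 + 1 = 730 days.
- No earlier flare, end on Day -30: -30 + 730 + 1 = 701 days.
- Interim window, end on Day -1: -1 + 336 + 1 = 336 days.

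**Merging, for a flare that ends on Day -30.**

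| Preceding flare | Imputed start | Duration | Same-eye gap | Merged? |
|---|---|---|---|---|
| Same eye, ended Day -600 | -600 | 571 | 0 | Yes |
| Same eye, ended Day -819 | -730 | 701 | 89 | Yes |
| Same eye, ended Day -820 | -730 | 701 | 90 | No |
| Same eye, ended Day -1000 | -730 | 701 | 270 | No |
| Same eye ended Day -600, other eye ended Day -400 (literal text) | -400 | 371 | 200 | No |

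In the first row the two flares merge whatever the true gap was. In the second row the merged episode begins before the window.

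**Effect of lost historical episodes.** Design inputs (Protocol 12.8, SAP 2.4) are 86 subjects, 29.2 and 14.6 flares per 100 subject-years, and 1.5 years of average follow-up. Expected historical episodes over 2 years are 86 × 2 × 0.292 = 50.2. If k are lost to merging, the rate ratio is 0.146 / [(50.224 - k) / 172]:

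- k = 0: 0.50
- k = 1: 0.51
- k = 2: 0.52
- k = 5: 0.56

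**Effect on study.** Expected on-study flares are 86 × 1.5 × 0.146 = 18.8. If one is absorbed into an existing pre-study episode, the ratio is (17.834 / 129) / 0.292 = 0.47. As an example, take an on-study flare that ends on Day 400 with no start date, and a same-eye pre-study flare that ended on Day -30. The imputed start is Day 0 and the gap is 30 days, so the flare leaves the on-study count.

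**Effect on historical flare-days.** The documents give no typical duration, so I assumed a true mean d of 21, 42 or 90 days. I also assumed one affected flare with no earlier flare in the window and an end date uniform over the 730 days. Its mean imputed duration is (1 + 730) / 2 = 365.5 days. Total historical flare-days are 50.224 × d, and the added share is (365.5 - d) / (50.224 × d):

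- d = 21: 344.5 / 1055 = 33%
- d = 42: 323.5 / 2109 = 15%
- d = 90: 275.5 / 4520 = 6%

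**The case against.** Much of the case on the other side stands.

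- **Frequency.** Nothing in the documents shows that any flare has a known end date and no start year. The 6% to 33% range depends on one existing and on the assumptions listed with it.
- **Primary endpoint.** Stretching a start date does not by itself change an episode count. Pre-study merging is conservative for the rate ratio. The on-study route that favours CZP needs a prospectively recorded flare with no start date at all, plus a same-eye flare that ended less than 90 days before first dose.
- **Existing safeguard.** SAP 8.1.2 also analyses flares as the investigators reported them, without the 90-day correction. That partly covers the count effects in both directions. It does nothing for duration.
- **Status of the variable.** SAP section 8 makes everything beyond the primary analysis exploratory. The planned summaries include a median, which one outlier hardly moves.
- **Same-eye wording.** The Amendment 3 entry in SAP 13.3 gives this sentence with the same-eye restriction, so its absence from the current 4.2 looks editorial.

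Two stronger readings are tempting, and neither is supported. A reader might infer that such a flare always merges with an earlier same-eye flare. It does not if that flare ended 90 days or more before the window. On the literal text it also does not if an other-eye flare ended later and at least 90 days after it. A reader might also infer that the rule biases the primary result towards CZP. The historical effect runs the other way, and the on-study effect needs a rare combination.

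None of this explains why a missing end date is capped at the subject's own median while a missing start date is left open.

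**Conclusion.** The point holds in a limited form. Followed as written, SAP 4.2 can record a single historical flare as lasting up to 730 days. It also forces a merge with an immediately preceding same-eye flare that ended inside the window. The plan already has the remedy for the mirror case and gives no reason for treating the two differently.

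The main consequence is for the exploratory flare-duration summary. The primary count is affected only through merging, by about 0.01 in the rate ratio for each historical episode lost (against CZP) and about 0.03 for an on-study episode absorbed (towards CZP). These sizes rest on the design rates and on at least one such flare occurring. The true number may be small or zero. The rule should be corrected because it gives wrong values whenever it is used, but it does not threaten the trial's main conclusion.

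**What to change.** In SAP 4.2, set a completely missing start date to the latest of:

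- (a) the window start (on study: the first dose date);
- (b) the day after the end of the previous flare in the same eye;
- (c) the end date minus the subject's median flare duration plus 1.

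Use the median that 4.2 already defines, with the pooled median where a subject has no completely dated flare. Restore the same-eye restriction to the pre-study sentence, as in the Amendment 3 entry. Extend the 8.1.2 sensitivity analysis that drops subjects with completely missing end dates to those with completely missing start dates.

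For a flare ending on Day -30 with assumed medians of 28, 42 or 84 days, the start becomes Day -57, -71 or -113, and the recorded duration equals the median. The gap to a same-eye flare that ended on Day -600 becomes 543, 529 or 487 days, so the two stay separate.

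The floor in (a) is needed. With a 42-day median and no floor, a flare ending on Day -720 would start on Day -761 and leave the historical count. One ending on Day 20 would start on Day -21 and leave the CZP count. The floor has one limit, which the current rule shares: a flare that in fact began before the window is still counted.

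The cost is SAP wording and a little extra derivation code. No new data are needed, and if no such flare exists no result changes.
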